### **Safety Analyses**

Adverse event and drug reaction outcomes will be presented using standard summary statistics.

AEs will be mapped to system organ classes and preferred terms in MedDRA. Treatment emergent events are defined as those that start or worsen after the start of study treatment and up to 28 days after the last dose of study treatment. AEs will be summarized by treatment group, system organ class, and preferred term, and also by event severity and by the event's relationship to study treatment. At each level of summation, subjects will be counted only once, under the greatest severity and strongest study-drug relationship (as reported by the investigator).

Clinical laboratory data will be summarized for each treatment group at each measurement time point and for each subjects final post-Baseline measurement in the following ways: (1) with descriptive statistics (mean, standard deviation, median, and range) for each

measurement time point; (2) with descriptive statistics for the change from Baseline in the measurements at each post-Baseline time point; and (3) with shift tables summarizing the frequencies of patients below, within, and above the normal ranges at each time point as compared with Baseline. All clinical laboratory values collected during the study will be listed, with values outside the normal ranges flagged for clinical evaluation. Grade 3 and 4 laboratory results will be listed and summarized. Vital signs will be summarized by treatment group and listed for each patient. Concomitant medications will be summarized by treatment group based on mapping to drug classes and generic terms in the WHO Drug Dictionary.

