5. Candidate biomarker expression in the peripheral blood of patients with HP over the 52-study follow-up period.

*Safety Outcome Measures:*

1. Proportion of patients with treatment-emergent adverse events (AEs)
2. Proportion of patients with treatment-emergent serious adverse events (SAEs)
3. Proportion of patients with treatment-emergent adverse drug reaction (ADRs)
4. Proportion of patients with treatment-emergent serious drug reaction (SDRs)
5. Proportion of patients with AEs leading to early discontinuation of study treatment
6. Proportion of patients with treatment-emergent deaths
7. Proportion of patients with treatment-emergent changes in clinical laboratory findings, vital signs and ECGs.

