**Early Discontinuation of Study Treatment**

Subjects who discontinue study treatment before Week 52 will complete a Follow-up Visit. In addition to the procedures listed above for the Follow-up Visit, subjects who discontinue study treatment before Week 52 must return all used and unused study treatment. Subjects who discontinue study treatment will be asked to continue to complete all scheduled study assessments and procedures through Week 52.

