## **Adverse Event Reporting Period**

The study period during which all AEs and SAEs as described in *section J* where the patient has been exposed to Genentech product must be reported begins after informed consent is obtained and the initiation of study treatment and ends 28 days following the last administration of study treatment or study discontinuation/termination, whichever is earlier. After this period, investigators should only report SAEs that are attributed to prior study treatment.

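### Safety counting and most reporting end 28 days after the last dose while subjects who stop drug are followed to Week 52, so crude SAE and late-AE proportions rest on unequal patient time if stopping differs by arm

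*Combined protocol and SAP*

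**What the plan says.** **Counting.** Safety Outcome Measures (under Study Endpoints) lists treatment-emergent AEs, SAEs, drug reactions and deaths as proportions of patients. Safety Analyses defines treatment-emergent events as those that "start or worsen after the start of study treatment and up to 28 days after the last dose of study treatment". On method it says "Adverse event and drug reaction outcomes will be presented using standard summary statistics" and "At each level of summation, subjects will be counted only once". It plans no patient-time, exposure-adjusted rate, cumulative incidence, or AE/SAE table running to Week 52 for all treated subjects.

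**Reporting.** Adverse Event Reporting Period says the period "ends 28 days following the last administration of study treatment or study discontinuation/termination, whichever is earlier". It continues: "After this period, investigators should only report SAEs that are attributed to prior study treatment".

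**Follow-up.** Early Discontinuation of Study Treatment says "Subjects who discontinue study treatment will be asked to continue to complete all scheduled study assessments and procedures through Week 52". The visit lists for Weeks 5, 13, 26, 39 and 52 each include a review of AEs/SAEs and hospitalizations and are not limited to subjects on drug. The section on methods and timing for recording safety variables makes the study team responsible for collecting every AE and SAE observed or reported during the study.

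**Related outcomes.** All-cause mortality and all-cause hospitalization are key secondary efficacy outcomes with no 28-day limit.

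**The concern.** Two problems follow.

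The first is a conflict over recording. Take a subject who stops at Week 10 and has an SAE judged unrelated at Week 40. The visit schedule asks about the event, and the general collection rule says it is collected. The reporting-period section says such events need no report once the window has closed. A site following that section could leave the event out of the database, and no later analysis would recover it.

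The second is a denominator that ignores time. The Week 10 stopper can contribute an event for about 14 weeks and a completer for 52, yet each is one subject in the same proportion. Even an SAE attributed to study drug at Week 40 would be reportable for that stopper but would fall outside the treatment-emergent proportion.

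Safety and tolerability of pirfenidone is one of the two stated objectives. If one arm stops drug more often, its proportions cover less follow-up and come out lower at equal true risk.

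**Working it through.** **Inputs from the protocol.** Window: last dose + 4 weeks. Follow-up: 52 weeks. Randomization: 42 subjects at 2:1, so about 28 vs 14. The protocol states no SAE rate and no stopping rate by arm, so there is no planned figure to reproduce. The 10% under Sample Size and Power Considerations is overall attrition.

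**Assumptions.** Share stopping (pirfenidone vs placebo) *d*₁ vs *d*₀: 15% vs 7%, 20% vs 7%, 30% vs 10%. Stopping at Week *m* = 13 or 26, with Week 8 as a sensitivity. SAE hazard *h* = 0.20 to 0.35 per year, the same in both arms. Time is capped at Week 52.

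**Step 1: counted weeks per stopper**, *m* + 4. Stopping at Week 4, 13, 26 or 39 gives 8, 17, 30 or 43 weeks, which is 15%, 33%, 58% or 83% of 52.

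**Step 2: share of 52-week patient time counted**, (1 − *d*) + *d*(*m* + 4)/52. At *m* = 13:
- 20%: 0.80 + 0.20 × 17/52 = 86.5%; 7%: 0.93 + 0.07 × 17/52 = 95.3%.
- 30%: 0.70 + 0.30 × 17/52 = 79.8%; 10%: 0.90 + 0.10 × 17/52 = 93.3%.

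**Step 3: artificial difference when stopping is unrelated to the event.** With equal hazards,

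shift = (*d*₁ − *d*₀) × [exp(−*h*(*m* + 4)/52) − exp(−*h*)].

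| *h* | Stopping | Week | Calculation | Shift (points) |
|---|---|---|---|---|
| 0.20 | 15% vs 7% | 26 | 0.08 × (0.8910 − 0.8187) | 0.6 |
| 0.20 | 15% vs 7% | 13 | 0.08 × (0.9367 − 0.8187) | 0.9 |
| 0.20 | 20% vs 7% | 13 | 0.13 × (0.9367 − 0.8187) | 1.5 |
| 0.35 | 30% vs 10% | 13 | 0.20 × (0.8919 − 0.7047) | 3.7 |

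**Step 4: upper end, with frailer subjects stopping.** Suppose 30% of each arm carries three times the hazard (1.05 per year), the rest have 0.35, and all stoppers come from the frail 30%. The 52-week risks are 0.295 (others) and 0.650 (frail); over 17 weeks a frail subject's risk is 0.291.
- True Week 52 risk, both arms: 0.70 × 0.295 + 0.30 × 0.650 = 40%.
- Counted, 30% stopping: 0.70 × 0.295 + 0.30 × 0.291 = 29.4%.
- Counted, 10% stopping: 0.70 × 0.295 + 0.20 × 0.650 + 0.10 × 0.291 = 36.6%.
- Shift: 7.2 points. Stopping at Week 8 instead of Week 13 raises it to 0.20 × (0.7848 − 0.3499) = 8.7 points.

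**Step 5: what shrinks it.** Take a 52-week risk of 20% and 30% vs 10% stopping at Week 13.
- Constant hazard: 16.1% vs 18.7%, a shift of 2.6 points, or 0.026 × 28 ≈ 0.7 of a patient.
- If 80% of the cumulative hazard falls in the first 17 weeks: 18.9% vs 19.6%, a shift of 0.7 points.
- If the counted event is itself the reason for stopping, it is already counted and the loss is zero.

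**Step 6: scale.** The standard error of the arm difference at 20% risk is √[0.20 × 0.80 × (1/28 + 1/14)] = 13.1 points. At the 40% risk of Step 4 it is about 16 points.

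**Step 7: counting to Week 52.** If all treated subjects are counted to Week 52 whatever their drug status, both arms cover 52 of 52 weeks and the artificial difference is zero under equal hazards.

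**The case against.** A reader might infer that safety ascertainment stops 28 days after the last dose. The documents do not support that. AE/SAE review continues at visits to Week 52, the general rule says all observed events are collected, and attributed SAEs stay reportable. What ends is the treatment-emergent count and the requirement to report other events.

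A reader might also infer that pirfenidone will look safer than it is. That is not supported either. No stopping rate by arm is given, and the listed reasons for stopping include patient request, investigator discretion and lung transplantation, which need not be commoner on pirfenidone. Subjects who stop because of an AE already count as having one, and AEs leading to discontinuation are tabulated separately.

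The rest of the opposing case has weight. A treatment-emergent summary with a fixed post-dose window is a legitimate on-treatment measure and is labelled as such. Safety is descriptive, so no planned test is biased. The shift is within sampling error in a trial of this size. Death and hospitalization to Week 52 capture many SAEs.

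These arguments limit the size of the problem without removing it. Death and hospitalization do not cover SAEs that qualify only through life threat, disability or medical significance, or any non-serious AE. The shift is systematic, whereas the standard error measures chance. The conflict over recording stands whatever the stopping rates turn out to be.

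**Conclusion.** The point holds as a conditional weakness that is cheap to repair. The sections on reporting period, visit content and general collection conflict on whether unattributed events more than 28 days after the last dose are recorded. Separately, crude proportions give less counted time to whichever arm stops drug more, which understates its SAE and late-AE proportions if stopping differs by arm.

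The size is roughly 0.6 to 7 points for stopping of 15% vs 7% to 30% vs 10% around Weeks 13 to 26 and SAE hazards of 0.20 to 0.35 per year. All of these rates are assumptions. The lower end has stopping unrelated to risk. The upper end needs the widest stopping gap, the highest hazard and stoppers at three times that hazard; without that threefold excess the largest value is 3.7 points. The shift falls below 1 point with strongly front-loaded events at 20% risk, and is zero for events that cause stopping. Its direction cannot be known from the documents.

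**What to change.** **Recording.** Reconcile Adverse Event Reporting Period with the visit lists and the general collection rule. State that, for subjects still attending study visits, all SAEs are recorded in the study database through Week 52 regardless of attribution. The reporting period to the drug supplier can stay as it is.

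**Analysis.** In Safety Analyses, keep the treatment-emergent tables and add:
- (a) patient-time by arm and exposure-adjusted incidence: subjects with a first event divided by patient-time at risk in the treatment-emergent window;
- (b) a descriptive by-arm table of SAEs from first dose to Week 52 regardless of treatment status.

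**Cost.** Protocol and analysis wording plus two tables. The events are already asked about at scheduled visits, so no new visit or procedure is needed. The drawback is that some off-drug events enter table (b), so it should be read beside the treatment-emergent table. The recording change matters most while subjects are still being followed, since unrecorded events cannot be restored at analysis.

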### **Trial Monitoring**

Throughout the study, the safety officer will review individual SAE reports and laboratory toxicities. In addition, the safety officer will review all safety data after 50% of enrollment is completed as well as SAEs on an ongoing basis. At all times during the course of the study, the safety officer may request access to unblinded data if needed.

## **SAFETY REPORTING OF ADVSERSE EVENTS**

### **Assessment of Safety**

### **Specification of Safety Variables**

Safety assessments will consist of monitoring and reporting adverse events (AEs) and serious adverse events (SAEs) per protocol. This includes all events of death, and any study specific issue of concern.

### **Adverse Events**

An AE is any unfavorable and unintended sign, symptom, or disease temporally associated with the use of an investigational medicinal product (IMP) or other protocol-imposed intervention, regardless of attribution.

This includes the following:

1. AEs not previously observed in the subject that emerge during the protocol-specified AE reporting period, including signs or symptoms associated with FHP that were not present prior to the AE reporting period.
2. Complications that occur as a result of protocol-mandated interventions (e.g. procedures such as 6 Minute Walk Test).
3. If applicable, AEs that occur prior to assignment of study treatment associated with medication washout, no treatment run-in, or other protocol-mandated intervention.
4. Preexisting medical conditions (other than the condition being studied) judged by the investigator to have worsened in severity or frequency or changed in character during the protocol-specified AE reporting period.

## **Serious Adverse Events**

An AE should be classified as an SAE if the following criteria are met:

1. It results in death (i.e., the AE actually causes or leads to death).
2. It is life threatening (i.e., the AE, in the view of the investigator, places the subject at immediate risk of death. It does not include an AE that, had it occurred in a more severe form, might have caused death.).
3. It requires or prolongs inpatient hospitalization.
4. It results in persistent or significant disability/incapacity (i.e., the AE results in substantial disruption of the subject's ability to conduct normal life functions).
5. It results in a congenital anomaly/birth defect in a neonate/infant born to a mother exposed to the IMP.
6. It is considered a significant medical event by the investigator based on medical judgment (e.g., may jeopardize the subject or may require medical/surgical intervention to prevent one of the outcomes listed above).

## **Methods and Timing for Assessing and Recording Safety variables**

The study team is responsible for ensuring that all AEs and SAEs that are observed or reported during the study, are collected and reported to the FDA, appropriate IRB(s), and Genentech, Inc. in accordance with CFR 312.32 (IND Safety Reports).

## **Adverse Event Reporting Period**

The study period during which all AEs and SAEs as described in *section J* where the patient has been exposed to Genentech product must be reported begins after informed consent is obtained and the initiation of study treatment and ends 28 days following the last administration of study treatment or study discontinuation/termination, whichever is earlier. After this period, investigators should only report SAEs that are attributed to prior study treatment.

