### **Physical Exam and Vital Signs**

A complete physical examination will be performed by a study physician and will include all body systems pertinent to the subject. If clinically significant abnormalities are observed before Day 1, they will be reported in the patient's medical history. If clinically significant abnormalities are observed after Day 1, the investigator will decide if they are new adverse events. Vital signs for this study protocol include heart rate, blood pressure, oxygen saturation and FiO2.

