### **Washout Period (28 Days)**

Before entering a subject in the Washout Period, all relevant medical history, diagnostic findings, and measures of disease severity should be reviewed to evaluate the subject's suitability for the study. Written informed consent must be obtained before withdrawing or tapering the subject off prohibited therapies. The study team must explain to the subject that entry into the study is not guaranteed. Any subject identified for the study must

discontinue all prohibited medications at least 28 days before Screening. This is the Washout Period. If a medication must be tapered, tapering must start early enough that the subject has discontinued the drug 28 days before the start of Screening.

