#### **Before Randomization**

1. Directed history (including review of AEs/SAEs, concomitant medications, oxygen use, and hospitalizations).
2. Physical examination, vital signs, FiO2 and weight.
3. Clinical laboratory assessments, including hematology, serum chemistries, pregnancy test for women of childbearing capacity.
4. Spirometry (FVC, FEV1) and DLCO.
5. 6MWT with Borg Scale pre and post.

6. UCSD SOBQ, L-IPF and SGRQ.
7. Confirmation of patient eligibility for study participation.
8. Genetic testing (RNA-seq and ChIP-seq).

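### Mandatory AE/SAE reporting starts only at first dose, although the protocol counts washout- and procedure-related events before treatment assignment as adverse events

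*Combined protocol and SAP*

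**What the plan says.** All references are to the combined protocol and SAP.

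- **Adverse Event Reporting Period.** The period in which AEs and SAEs "must be reported begins after informed consent is obtained and the initiation of study treatment". The same sentence limits the events to those "where the patient has been exposed to Genentech product". The only provision for events outside the period concerns SAEs after it ends.
- **Adverse Events.** The definition includes "Complications that occur as a result of protocol-mandated interventions" (item 2, with the 6-minute walk test as its example) and, if applicable, "AEs that occur prior to assignment of study treatment associated with medication washout, no treatment run-in, or other protocol-mandated intervention" (item 3).
- **Washout Period (28 Days).** Prohibited drugs must be stopped at least 28 days before Screening. "Written informed consent must be obtained before withdrawing or tapering the subject off prohibited therapies". Candidates are also to be warned that they may not be enrolled.
- **Physical Exam and Vital Signs.** Clinically significant abnormalities found at examination before Day 1 are filed as medical history.
- **Before Randomization (Day 1).** The first procedure is "Directed history (including review of AEs/SAEs, concomitant medications, oxygen use, and hospitalizations". The Screening Period list has no AE review.
- **Methods and Timing for Assessing and Recording Safety Variables**, and **Assessment of Adverse Events.** Both state a general duty to report AEs and SAEs arising in the study. Neither says when that duty starts.
- **Deaths** (item b of the recording instructions). Reporting of deaths is tied to the protocol-specified reporting period.

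**The concern.** The trial itself creates the washout risk. Medication Exclusions lists, among others, methotrexate, tacrolimus, cyclosporine, bosentan, ambrisentan and daily sildenafil. A patient taking one of these gives consent and stops or tapers it in order to qualify, with no assurance of being randomized. The condition that item 3 of the AE definition applies only where relevant is therefore met.

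If the timing rule is followed literally, a serious event during that withdrawal falls outside required SAE reporting, and a death falls outside required death reporting. The safety officer reviews individual SAE reports (Trial Monitoring), so an event that need not be reported may not reach that review. Because the sections disagree, two coordinators at the centre could handle the same event differently and each cite the protocol.

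**Working it through.** This is a comparison of texts. The only arithmetic is the length of the uncovered interval.

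**Can an item 3 event fall inside the reporting period?** Item 3 events occur before treatment assignment. Randomization is at the end of Day 1, and dosing starts that day, after randomization. The reporting period requires consent and the start of dosing. Every item 3 event therefore begins before the period opens, so the protocol defines a class of AE that its own reporting period cannot contain.

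**Does another section supply an earlier start?**

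- The general duty in Methods and Timing has no dosing condition, but also no start date. If it governs, the timing rule is wrong. If the timing rule governs, item 3 has no effect.
- The Day 1 AE review shows that pre-dose events were meant to be looked for. It reaches only subjects who get to Day 1.
- The Deaths item inherits the same period, so it adds no earlier start.

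**Length of the uncovered interval after consent.** Inputs: washout of at least 28 days (Washout Period); screening of up to 30 days (Study design, Screening Period, and Eligibility and Randomization) or up to 4 weeks = 28 days (Study Assessments).

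- Washed-out subject, 30-day screening: 28 + 30 = 58 days.
- Washed-out subject, 4-week screening: 28 + 28 = 56 days.
- With a taper: longer by the length of the taper, because consent precedes tapering and the 28 days count from the last dose of the withdrawn drug.
- No washout: up to 30 days (28 on the 4-week figure).
- Washed out and then fails screening: no dose is given, so no part of the subject's participation is covered.
- Period opened at consent for these events: 0 days uncovered.

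**Procedures.** Six 6-minute walk tests are scheduled (Screening, Day 1, Weeks 13, 26, 39 and 52). The Screening and Day 1 tests, 2 of 6, precede the first dose. The Day 1 test is on the same day as that dose, so it adds little uncovered time.

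**The case against.** The strongest reply is that the protocol elsewhere makes the study team responsible for reporting all AEs and SAEs seen during the study, and that the timing rule sets when reporting is mandatory without forbidding earlier reporting. That stands. A reader might infer that washout harm will go unreported. The documents do not support this; they show only that the stated period does not require the report.

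It can also be said that the timing rule, with its reference to product exposure, governs only exposed subjects and leaves the rest under the general duty. That reading is possible. But the section title carries no such restriction, no other start date exists, and the Deaths item and items 1 and 4 of the AE definition rely on the same period. At best the scope is unclear.

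Three further inferences go too far:

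- That a hospitalization before Day 1 becomes medical history. The sentence concerned sits under Physical Exam and Vital Signs and covers abnormalities found there. It says nothing about SAEs.
- That the safety officer is shut out before dosing. Trial Monitoring describes review throughout the study. The weakness lies in whether a report has to be made.
- That different sites would diverge. The study is single-centre.

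Finally, prednisone, azathioprine and mycophenolate are permitted therapies, so many candidates may need no washout. That is a fair limit on the number affected, which cannot be estimated from the documents.

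**Conclusion.** The inconsistency is real and should be corrected. Events before the first dose that are related to washout or a protocol procedure are AEs by definition, yet reporting them is not required under the stated period, and the general duty elsewhere conflicts with that period without settling the matter. The uncovered time is up to 56 to 58 days per washed-out subject with the minimum washout and the longest screening allowed, more with a taper, and up to about 30 days for others. No count of subjects or events can be given, because the documents do not say how many will need washout.

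The gap matters most for the subject who is washed out, has a serious event and fails screening, since neither the reporting period nor the Day 1 AE review is ever reached. The point concerns the protection of participants before treatment. It has no bearing on the efficacy analysis or on the comparison of treatment-emergent events.

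**What to change.** Reconcile the five sections that now disagree:

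1. **Adverse Event Reporting Period.** Open the period at informed consent, including consent given for washout, for SAEs and AEs related to washout or another protocol-mandated procedure. State that screen failures are included. From first dose, require all AEs and SAEs. Remove or reword the product-exposure condition so that it does not cancel the first step.
2. **Adverse Events.** Point items 2 and 3 to that start.
3. **Methods and Timing for Assessing and Recording Safety Variables.** Refer to the same period, so that the general duty and the timing rule agree.
4. **Deaths.** Apply the same start.
5. **Physical Exam and Vital Signs.** State that an abnormality arising after consent and related to washout or a study procedure is recorded as an AE.

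Leave the treatment-emergent definition under Safety Analyses as it is. The cost is protocol wording and a few extra pre-treatment report forms. The report form should allow an event to be attributed to washout or a procedure, since the present causality guidance addresses only the study drug. No analysis changes.
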